7.1 Drugs Used as Part of the Protocol

603

Participants will use their own Humalog (insulin lispro) or Novorapid (insulin aspart) during the Run In and Treatment Period with the study devices.

605

7.2 Collection of Medical Conditions and Medications

606

Pre-Existing Conditions: Any medical condition that is either present at screening, a chronic disease, or a prior condition that could impact the participant's health during the course of the study (e.g., prior myocardial infarction or stroke) will be recorded.

609

Medical Conditions Developing During the Study: Medical conditions developing during the study will be reviewed by the investigator for their relationship to the study device.

611

Medications: All medications in use at the time of screening or added during the course of the study will be recorded. Nutraceuticals and preventative treatment also will be recorded. Medications only taken as needed either can be recorded when prescribed or only recorded if used during the study. Glucagon for treatment of severe hypoglycemia will only be recorded if used during the study.

615

7.3 Prohibited Medications, Devices, Treatments, and Procedures

616

Treatment with any insulin other than Humalog or Novorapid insulin with the study pumps is not permitted. Treatment with a non-insulin glucose -lowering agent, other than metformin, is not permitted, including GLP-1 receptor agonists, Symlin, DPP-4 inhibitors, SGLT-2 inhibitors, or sulfonylureas.

619

The investigational study device (t:slim X2 insulin pump with Tandem Freedom algorithm) and study sensor and transmitter (Dexcom CGM sensor and transmitter) must be removed before magnetic resonance imaging (MRI), computed tomography (CT), X-Rays, or diathermy treatment. Participants may continue in the trial after temporarily discontinuing use if requiring one of the above.

623

7.4 Rescue Medications, Treatments, and Procedures

624

Each participant will be required to have a glucagon preparation for rescue therapy for severe hypoglycemia.

626

7.5 Pregnancy Reporting

627

If pregnancy occurs, the participant will be discontinued from the study. The occurrence of pregnancy will be reported to the Coordinating Center within seven days and to the HDEC as an Unanticipated Problem within seven calendar days.

630

7.6 Participant Compensation

631

Participant compensation will be specified in the informed consent form.

632

7.7 Participant Withdrawal

633

Participation in the study is voluntary, and a participant may withdraw at any time. For participants who withdraw, their data will be used up until the time of withdrawal.

635

636

Chapter 8: Statistical Considerations

637

8.1 General Statistical Considerations

638

Summary statistics will be generated for all relevant variables. In the comparison of continuous variables, distributions will be tested for the normality assumption. If standard parametric techniques are found to be inadequate, an appropriate non-parametric technique will be used. Categorical variables will be presented using frequencies and percentages and compared using differences in proportions unless stated otherwise. For safety/adverse event reporting, both the number of overall events and the number of participants experiencing that event will be tabulated. No corrections will be made for multiple testing procedures.

644

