Protocol Identifying Number:	TP-0020402
Protocol Name:	Tandem Freedom Feasibility Trial #2
Protocol Version / Date:	1.0 / 20 NOV 2024

The Principal Investigators (undersigned) hereby declare that they have read this protocol and agree to its contents.

The investigator agrees that the study will be conducted according to the applicable New Zealand regulations (Medsafe and Health and Disability Ethics Committee), International Conference on Harmonization (ICH) guidelines on Good Clinical Practice (GCP) and the principles of the World Medical Association Declaration of Helsinki 2008. The investigator will conduct all aspects of this study in accordance with all national, state, and local laws or regulations.

By written consent to this protocol, the investigators agree to the above and to fully co-operate with all monitoring and audits in relation to this trial by allowing direct access to all documentation, including source data, by authorized individuals representing Tandem Diabetes Care, Inc., HDEC, Medsafe New Zealand, and/or by the US Federal, State and local regulatory authorities.

Investigator Name: _____

Investigator Signature: _____

Date (DD/MMM/YYYY): _____

PROTOCOL SUMMARY

[figure not shown]
Study Sponsor	Tandem Diabetes Care, Inc.
Protocol Number	TP-0020402
Protocol Title	Tandem Freedom Feasibility Trial #2
Précis	This feasibility study is a prospective, single arm study evaluating the Tandem Freedom system compared to a Control-IQ technology run-in phase in adults with type 1 diabetes. Existing Control-IQ technology users will use Control-IQ technology at home for 1 week, then will use Tandem Freedom in a supervised hotel setting with Dexcom follow active. The goal of Tandem Freedom is to use the system without requiring meal boluses.
Products	Investigational Device: t:slim X2 insulin pump with Tandem Freedom Algorithm
Objectives	The objective of the study is to assess the feasibility of the Tandem Freedom system, by assessing safety and performance in a short-term supervised setting in adults with type 1 diabetes under direct clinical supervision.
Number of Sites	1 Clinical Site in New Zealand
Study Design	Single arm, prospective feasibility study to assess safety.
Number of Participants	Up to 20 participants signing consent to use the study devices, with a goal that at least 10 complete the study.

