	
 9. History of allergic reaction to Humalog or Novorapid 10. Use of any medications determined by investigator to interfere with study 11. Significant chronic kidney disease (which could impact continuous glucose monitoring (CGM) accuracy in investigator's judgment) or hemodialysis 12. Concurrent use of any medication that could interfere with the study CGM, such as hydroxyurea 13. History of adrenal insufficiency 14. History of abnormal TSH consistent with hypothyroidism or hyperthyroidism that is not appropriately treated 15. History of gastroparesis 16. A condition, which in the opinion of the investigator or designee, would put the participant or study at risk 17. Participation in another pharmaceutical or device trial at the time of enrollment or anticipated for during the time period of study participation 18. Employed by, or having immediate family members employed by Tandem Diabetes Care, Inc., or having a direct supervisor at place of employment who is also directly involved in conducting the clinical trial (as a study investigator, coordinator, etc.); or having a first-degree relative who is directly involved in conducting the clinical trial
Participant Duration	Approximately 2 weeks

Study Endpoints	
The two study periods are:
 
 1) Control-IQ run-in period 2) The Tandem Freedom hotel observed period 
Primary Endpoints for each period:
 
 1. Number of severe hypoglycemia events (with cognitive impairment such that assistance of another individual is needed for treatment) 2. Number of diabetic ketoacidosis events 
Secondary Endpoints for each period:
 
 1. All device-related adverse events 2. CGM hypoglycemia outcomes 
 a. Overall % time <3.0 mmol/L b. Overall % time <3.9 mmol/L 3. Times in ranges-overall (3.9 - 10.0 mmol/L, >10.0 mmol/L, >13.9 mmol/L, 3.9 - 7.9 mmol/L) 4. Mean glucose 5. Glycemic variability (CV and SD) 
Due to the small sample size and feasibility nature of the study, primarily descriptive statistics will be used.

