3.1 Visit 2: Start Control-IQ Run-In

211 After screening, participants will have a clinic visit at which they will be given the study CGM (Dexcom
212 G6) and begin the run-in period. The run-in period will be 7 +/- 3 days.

213 This device training visit should be completed within 2 weeks of screening, and may be performed the
214 same day as the screening visit. If not completed within 2 weeks of screening, re-review of screening
215 results by the investigator should be performed, who may ask for repeated testing as per investigator
216 judgement. The device training visit must occur in clinic and cannot be performed remotely.

217 Participants will receive additional supplies for blood glucose and ketone testing if needed.

218 Participants will continue to use their home insulin pump (t:slim X2 insulin pump with Control-IQ
219 technology) during the run-in phase. Participants will switch the CGM to the study provided CGM sensor
220 and transmitter.

221 Participants may contact study providers at any time for questions during the Control-IQ Run-In period.

222 Participants will be required to change their CGM sensor 48 +/- 12 hours before the hotel study.

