267 On Day 1, participants will arrive before lunch, where they will bolus for the lunchtime meal as per their
268 usual carb ratio and bolus routine with their home pump.

269 Participants will be switched the Tandem Freedom system and be encouraged to use the TruSteel infusion
270 set, waiting for at least 2 hours after lunch before starting the Freedom pump (Investigational Device).

271 Study staff will use the TDI from the last 7 days as shown on the participants home pump to initialize the
272 system, although they may adjust this value per clinical judgement, and re-initialize the system based on
273 an updated TDI at any time during the study.

274 A sleep schedule will be set from 11 PM to 6 AM so sleep activity automatically activates in the evening
275 and deactivates in the morning.

276 Participants will bolus for all meals for the remainder of Day 1, entering carbohydrates as they would
277 usually estimate and adjusting their overall bolus amount if needed.

278 Participants may perform low-intensity activity (e.g., walking) at any time during day 1.

279 No meals should occur after sleep activity is enabled.

280 **3.2.3 Days 2 through 4 – Full Days**

281 Sleep activity will be disabled upon waking up if not already automatically de-activated per the sleep
282 schedule.

283 On Days 2 - 4, participants will eat meals and snacks as they usually would, but will be encouraged to
284 NOT BOLUS for all meals and snacks. If a user or study staff feel a meal or correction bolus is needed,
285 the investigator will make this determination and allow for boluses as they determine are needed.

286 Participants will also be encouraged to perform a supervised brisk walk or similar exercise of at least 45
287 minutes each full day (Day 2 to Day 4) under staff supervision, at approximately the same time each day.
288 Additional exercise per the participants usual routine will be allowed as long as study staff are notified.
289 Exercise activity should be used for this exercise, to start 30-90 minutes before exercise, and turned off
290 after exercise is complete, as determined by the investigator.

291 Exercise does not have to be performed, but will be encouraged. Exercise will be cancelled or stopped at
292 any point for injury or development of new symptoms (development of chest pain/pressure, feeling
293 unwell, development of hypoglycemic symptoms, undue shortness of breath, signs of poor perfusion (leg

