294 pain/claudication), or any other symptoms, as determined by the investigator.

295 Participants may perform low-intensity activity (e.g., walking) at any time during the hotel study.

296 Supervised outings may occur with study staff present to areas outside of the hotel during the daytime.
297 Realtime CGM alerts will remain in place, and the same hypoglycemia/hyperglycemia treatment
298 guidelines apply as in the hotel setting.

299 No meals should occur after sleep activity is enabled.

300 **3.2.4 Day 5 – Morning**

301 Sleep activity will be disabled upon waking up if not already automatically de-activated per the sleep
302 schedule.

303 After waking up, participants will switch back to their home Control-IQ pump, and may have breakfast
304 prior to leaving the hotel.

305 Participants may be discharged if their CGM is ≥ 4.4 mmol/L for at least 15 minutes.

306 **3.3 Unscheduled Visits**

307 Participants may have unscheduled visits during the study run-in period if required for additional
308 questions or other unanticipated needs per the study investigator discretion.

309 At each contact, study staff will perform an:

- 310 • Assessment of device issues that have occurred
311 • Assessment of adverse events, using open ended questions to capture hyperglycemic and hypoglycemic
312 events during the Run-In Phase.

313

Chapter 4: Study Devices and Drugs

314

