8.4 Outcome Measures

651

The two study periods are:

652

1) Control-IQ at home run-in period.

653

2) The Tandem Freedom hotel observed period.

654

Primary Endpoints for each period:

655

1. Severe hypoglycemia (with cognitive impairment such that assistance of another individual is needed for treatment)

657

2. Number of diabetic ketoacidosis events

658

Secondary Endpoints for each period:

659

1. All device-related adverse events

660

2. CGM hypoglycemia outcomes

661

a. Overall % time <3.0 mmol/L

662

b. Overall % time <3.9 mmol/L

663

3. Times in ranges-overall (3.9-10 mmol/L, >10 mmol/L, >13.9 mmol/L, 3.9-7.9 mmol/L)

664

4. Mean glucose

665

5. Overall variability (CV and SD)

666

Due to the small sample size and feasibility nature of the study, primarily descriptive statistics will be used.

668

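### Section 8.1 reports per-period safety endpoints without participant-days, exposure-adjusted rates or intervals, although the Control-IQ run-in is about 1.1 to 2.7 times as long as Freedom use

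*Combined protocol and SAP*

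**What the plan says.** The Précis in the Protocol Summary describes the study as "evaluating the Tandem Freedom system compared to a Control-IQ technology run-in phase". Section 8.4 names two periods, the Control-IQ run-in and the Freedom hotel period. Under "Primary Endpoints for each period" it lists severe hypoglycemia and DKA; device-related adverse events are a secondary endpoint, also per period. Section 8.2 makes safety the primary objective, with no hypotheses and mainly descriptive outcomes.

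For these endpoints section 8.1 states: "For safety/adverse event reporting, both the number of overall events and the number of participants experiencing that event will be tabulated". Its general rule is: "Categorical variables will be presented using frequencies and percentages and compared using differences in proportions unless stated otherwise". Nothing in chapter 8 or elsewhere plans participant-days, a rate per unit of time or a confidence interval.

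Exposure is set out in chapter 3:
- The run-in is 7 ± 3 days, so 4 to 10 days (3.1).
- On Day 1 in the hotel, participants bolus for lunch on the home pump and switch to Freedom at least 2 hours later (3.2.1, 3.2.2).
- On Day 5: "After waking up, participants will switch back to their home Control-IQ pump, and may have breakfast" (3.2.4).
- One severe hypoglycemia or DKA event ends that participant's Freedom use (6.6.1). Table 1 in 3.2.1 also describes an immediate study stop after certain events. Data from withdrawals are used up to withdrawal (7.7).

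**The concern.** Two periods of different length are to be shown side by side, for a system described as compared with the run-in, using summaries that ignore time at risk. Raw counts grow with exposure. So do crude percentages and their differences, because a longer period gives each person more time to have an event. The period boundary is also loose: the hotel stay includes some Day 1 hours on the home pump, and 8.4 does not say to which system an event in those hours belongs.

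The second issue is separate and does not depend on unequal exposure. The earlier ten-participant study of this system had no severe hypoglycemia or DKA (1.1.2), so zero is a plausible result again. As planned, a zero on the primary safety endpoints would be reported with nothing to show how little it excludes.

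**Working it through.** The plan has no figure of its own to reproduce: 8.3 gives at least 10 completers as a convenience sample, with no power or precision target.

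**Inputs.** Run-in 4, 7 or 10 days (3.1). At least 10 completers (8.3) and up to 20 consenting (Protocol Summary). Freedom time is an assumption because the documents give no clock times: 15:00 on Day 1 to 07:00 on Day 5 = 88 h = 3.667 days. The 6 AM end of the sleep schedule (3.2.1) makes this end time reasonable.

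**1. Exposure ratio** = run-in days / Freedom days.
- 7 days: 7/3.667 = 1.91
- 4 days: 4/3.667 = 1.09
- 10 days: 10/3.667 = 2.73

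Other plausible clock times move this little. 14:00 to 09:00 (91 h, 3.79 days) gives 1.85 at 7 days; 17:00 to 06:00 (85 h, 3.54 days) gives 1.98. These are chosen times, not limits.

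**2. Freedom's share of all events at equal true rates** = Freedom days / (Freedom days + run-in days).
- 7-day run-in: 3.667/10.667 = 34%
- 4-day: 3.667/7.667 = 48%
- 10-day: 3.667/13.667 = 27%

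**3. Crude percentages carry the same distortion.** Take a rate of 1 per 100 participant-days in both periods, purely for illustration (no source in the documents). The expected proportion affected is 1 − exp(−0.01 × days): 3.6% on Freedom against 6.8% in a 7-day run-in.

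**4. Equal counts can mean unequal rates.** With 10 people and a 7-day run-in, exposure is 10 × 7 = 70 participant-days in the run-in and 10 × 3.667 = 36.7 on Freedom. One event in each gives 100/70 = 1.4 against 100/36.7 = 2.7 per 100 participant-days. That contrast comes from period length. If the event also ends the participant's Freedom use, or the study is stopped, Freedom participant-days fall below 36.7 and the rate rises further. The documents set no floor for this.

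**5. Precision of a zero.** The exact two-sided 95% upper limit for 0/n is 1 − 0.025^(1/n).
- n = 10: 30.8%
- n = 15: 21.8%
- n = 20: 16.8%

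Per unit of exposure, the exact Poisson limit at zero is −ln(0.025) = 3.689 divided by participant-days: 3.689/36.67 = 10.1 per 100 participant-days on Freedom, and 3.689/70 = 5.3 in a 7-day run-in. The binomial limit is the same in both periods for the same n, while the rate limit reflects exposure. The proportion therefore serves as a precision statement within a system, not as a comparison between systems.

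**The case against.** The strongest reply is that this is a single-arm, descriptive feasibility study. Section 8.2 sets no hypotheses, and neither the objective nor the rationale is worded as a comparison; the comparative phrase is in the Précis. Counts of events and of people affected are a usual summary at this size. A reader given 0 and 10 can work out 30.8%, and exposure could be recovered later from device files. If zero events recur, unequal exposure makes no difference.

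Part of this stands. The point is a gap in reporting and precision, not an error in a stated figure, and it calls for no power calculation. With zero events in both periods only the missing interval matters. But the endpoints are explicitly per period and 8.1 itself provides for differences in proportions, so a side-by-side reading is built in. Denominators and exact intervals are descriptive and fit 8.2.

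A reader might also infer that the planned tables will in fact favour Freedom. The documents do not support that. The direction in steps 2 and 3 assumes equal true rates and equal ascertainment. Run-in events reach staff through participants' calls (Schedule of Visits, footnote 3) and open-ended questions on hotel arrival, whereas the hotel is monitored around the clock (3.2.1). Unbolused meals and encouraged exercise could also raise Freedom counts, and at a 4-day run-in the imbalance nearly disappears.

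**Conclusion.** The gap is real and worth correcting before analysis. As written, the plan's comparison of safety events between systems takes no account of exposure that differs by a factor of about 1.9 at the nominal run-in and about 1.1 to 2.7 over the permitted window, and it attaches no precision to a zero. The ratio rests on the assumed 3.7 days of Freedom use. The limits of 30.8% and 16.8% apply to exactly 10 and 20 exposed participants.

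Three wider readings are not supported. Early termination of Freedom use after an event does not explain the 1.4 against 2.7 contrast, which is there from period length alone. The CGM endpoints expressed as percentages of time are not inflated merely by a longer period. Section 8.7 does not split device issues by period, so the exposure argument gives no ground for changing it.

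**What to change.** In 8.1 and 8.4:
1. Attribute each event to the system in use at onset, so Day 1 hours before the Freedom start count as Control-IQ.
2. Show participant-days on each system, with Freedom time ending at switch-back, discontinuation or a study stop.
3. Beside the planned counts, give events per 100 participant-days and use these for any comparison between systems. Label the limits approximate once an event has ended exposure, because the time at risk then depends on the outcome.
4. Give the proportion affected among all who started each system, with a Clopper-Pearson 95% interval, including at zero, and describe it as a within-system precision statement only.

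In 8.3, state the upper limit for zero events at the number actually exposed (30.8% if 10, 16.8% if 20).

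State that rates do not remove the difference between home and supervised hotel, or the difference in ascertainment.

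The cost is some wording and a few table rows. Start and stop times can come from the electronic device files (9.1) or be noted by staff on site. No participants or visits are added. The safety statement becomes more modest.

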8.2 Statistical Hypotheses

645

The primary objective of the study is assessment of safety. Therefore, there are no formal statistical hypotheses associated with any of the endpoints. Outcomes will be primary descriptive in nature.

647

8.3 Sample Size

648

The sample size of at least 10 participants completing the trial is required. As this is a feasibility study assessing safety, this sample size is for a convenience sample and is not based on a power analysis.

650

8.4 Outcome Measures

651

The two study periods are:

652

1) Control-IQ at home run-in period.

653

2) The Tandem Freedom hotel observed period.

654

Primary Endpoints for each period:

655

1. Severe hypoglycemia (with cognitive impairment such that assistance of another individual is needed for treatment)

657

2. Number of diabetic ketoacidosis events

658

Secondary Endpoints for each period:

659

1. All device-related adverse events

660

2. CGM hypoglycemia outcomes

661

a. Overall % time <3.0 mmol/L

662

b. Overall % time <3.9 mmol/L

663

3. Times in ranges-overall (3.9-10 mmol/L, >10 mmol/L, >13.9 mmol/L, 3.9-7.9 mmol/L)

664

4. Mean glucose

665

5. Overall variability (CV and SD)

666

Due to the small sample size and feasibility nature of the study, primarily descriptive statistics will be used.

668

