7 approaches to type 1 diabetes management.

8 1.1.2 Tandem X2 Insulin Pump and Tandem Freedom Control Algorithm

9 The Tandem X2 insulin pump with Control-IQ technology is an approved closed-loop control (CLC)
10 system. Use of the Control-IQ system has been extensively tested in adults and children with type 1
11 diabetes, demonstrating its efficacy and safety when used with insulin lispro (Humalog) or insulin aspart
12 (Novorapid).^{1,2} A recent evaluation of real-world use of the system in 9,451 users age \geq 6 years with at
13 least 12 months of system use found results comparable to those found in the randomized trials.³

14 A next generation CLC algorithm, the Tandem Freedom System, is now being evaluated to remove the
15 burden of meal bolusing. The system is designed to not require meal insulin boluses as part of its design.
16 This algorithm is now running in the t:slim X2 insulin pump.

17 A prior study with the Tandem Freedom system was completed in the supervised setting in New Zealand
18 in June 2024 (NCT06428591). Ten adults with type 1 diabetes (average age 30 years old [range 18 – 64
19 years old], duration of diabetes 18 +/- 13 years, total daily insulin 62 +/- 23 units/day [range 28 – 106
20 units/day], current Control-IQ users for 1.4 +/- 0.5 years, HbA1c 6.8 +/- 0.7% [range 6.0 – 7.9] completed
21 the study. After a Control-IQ run-in period at home, participants were admitted to the hotel for the
22 supervised study, where they used the Tandem Freedom system first with boluses for one day, then
23 without boluses for one, eating large meals and performing exercise each day.

24 The study showed participants achieved 61.8% time in range 3.9-10.0 mmol/L at home using Control-IQ
25 technology during the run-in week, 82.4% time in range 3.9-10.0 mmol/L using Freedom for 24 hours
26 with boluses, and 54.7% time in range 3.9-10.0 mmol/L using Freedom for 24 hours without meal
27 boluses. There were no severe hypoglycemia or DKA events, and no serious adverse events. As
28 participants were able to achieve nearly the same time in range without bolusing with Freedom as they
29 achieved with bolusing with Control-IQ, the results from this study support continued development and
30 evaluation in a second study.

31 1.2 Rationale

32 The objective of this study is to assess the feasibility of the Tandem Freedom system, by assessing safety

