33 and performance in a short-term supervised second feasibility study. The study will occur in a supervised,
34 hotel setting with medical staff present, with existing Control-IQ users with type 1 diabetes already
35 familiar with the t:slim X2 insulin pump, to further determine how Tandem Freedom functions with
36 unbolused meals and exercise.

37 1.3 Potential Risks and Benefits

38 Risks and Benefits are detailed below. Loss of confidentiality is a potential risk; however, data are
39 handled to minimize this risk. Hypoglycemia, hyperglycemia and ketone formation are always a risk in
40 participants with type 1 diabetes and participants will be monitored for these events. As all participants

41 will be existing Control-IQ users, and familiar with infusion set care and pump use, this helps to minimize
42 risk.

43 **1.3.1 Known Potential Risks**

44 **1.3.1.1 Blood Draw**

45 A venipuncture and/or fingerstick will be performed to obtain blood for HbA1c measurement.
46 Venipuncture can cause common reactions like pain, bruising, or redness at the sampling site.
47 Less common reactions include bleeding from the sampling site, formation of a small blood clot or
48 swelling of the vein and surrounding tissues, and fainting. A fingerstick frequently causes transient pain
49 and there may be a small, localized bruise, which may be followed by a small scar that may persist for
50 several weeks. The risk of local infection is less than 1 in 1000 with either venipuncture or fingerstick.

51 **1.3.1.2 CGM and Pump Catheter Risks**

52 There is a small risk of bleeding where the sensor or infusion set is inserted. There is a small risk for
53 developing a local skin infection at the site of Continuous Glucose Monitoring (CGM) sensor placement
54 and at the pump infusion set placement. This may be associated with swelling, redness and pain; and may
55 require antibiotic therapy. Rarely, a CGM sensor may break and leave a small portion of the sensor under
56 the skin that may cause redness, swelling or pain at the insertion site.

57 Some participants may develop skin irritation or allergic reactions to the adhesives used to secure the
58 CGM, or to secure the insulin infusion sets for the continuous subcutaneous insulin infusion. If these
59 reactions occur, different adhesives or “under-taping” (such as with IV 3000, Tegaderm, etc.) will be
60 tried, sites will be rotated frequently, and a mild topical steroid cream or other medication may be
61 required.

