8.5 Baseline Descriptive Statistics

669

Baseline demographic and clinical characteristics of the cohort of participants will be summarized in a table using summary statistics appropriate to the distribution of each variable.

671 **8.6 Additional Tabulations and Analyses**

672 The following data will be tabulated at baseline, for the run-in period, and for the hotel supervised period

- 673 • Insulin metrics (units/kg): total daily insulin, total daily manual insulin.

674 **8.7 Device Issues**

675 The following tabulations will be performed with respect to device issues:

- 676 • Number of device issues by type, and number of unique participants with each type of device issue

677 **8.8 Multiple Comparison/Multiplicity**

678 There are no adjustments performed for multiple comparisons.

679 **8.9 Handling of Missing Data**

680 All practical monitoring and follow-up steps will be taken to ensure complete and accurate data
681 collection. All analyses will be based on available data only; no imputation for missing data is planned.

682

683

Chapter 9: Data Collection and Monitoring

684

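### Hotel CGM and insulin results pool bolused Day 1 meals with Days 2–4, when meal boluses are discouraged, and no summary of the latter is planned

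*Combined protocol and SAP*

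**What the plan says.** Section 8.4 and the synopsis define two analysis periods, the Control-IQ run-in at home and "The Tandem Freedom hotel observed period". Every endpoint is given per period, and the range endpoints are labelled as overall values: "Times in ranges-overall (3.9-10 mmol/L, >10 mmol/L, >13.9 mmol/L, 3.9-7.9 mmol/L". Section 8.6 follows the same pattern: "The following data will be tabulated at baseline, for the run-in period, and for the hotel supervised period", with the content given as "Insulin metrics (units/kg): total daily insulin, total daily manual insulin".

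The bolus instruction changes inside the hotel period. Under Section 3.2.2, Day 1 lunch is bolused on the home pump. Freedom starts at least 2 hours later, and meals for the rest of that day are bolused on Freedom. Under Section 3.2.3, participants on Days 2–4 are encouraged not to bolus for meals or snacks, but the investigator may allow meal or correction boluses. Under Section 3.2.4 they return to the home pump on waking on Day 5.

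The stated interest is in the second condition. The précis says "The goal of Tandem Freedom is to use the system without requiring meal boluses" and describes the study as "evaluating the Tandem Freedom system compared to a Control-IQ technology run-in phase". Section 1.2 gives the purpose as "to further determine how Tandem Freedom functions with" unbolused meals and exercise. Section 1.1.2 reports the earlier study by bolus status: 82.4% time in range "with boluses, and 54.7% time in range 3.9-10.0 mmol/L using Freedom for 24 hours without meal" boluses, next to 61.8% on the Control-IQ run-in.

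**The concern.** An analyst who follows Sections 8.4 and 8.6 exactly produces one hotel figure per CGM endpoint and per insulin metric, and each figure mixes two conditions. No section plans a summary by day or by bolus instruction. The general statement in Section 8.1 that relevant variables will be summarised does not promise one.

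Three things are at stake, all in secondary descriptive outputs.

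- **Time in range.** If bolused meals give higher time in range, as in the earlier study, the pooled figure sits above the value for meals with boluses discouraged. The apparent distance to the run-in narrows.
- **Manual insulin.** This is the planned metric closest to showing how far meals went unbolused. Pooled, it includes the Day 1 dinner bolus that the protocol calls for, and that bolus cannot be told apart from boluses the investigator allowed later.
- **Period boundary.** Section 8.4 names a Freedom period and Section 8.6 a hotel period, while Section 3.2.2 has the hotel phase begin before Freedom is started. Whether the Day 1 home-pump hours count is not stated.

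**Working it through.** The documents give no expected hotel time in range, so there is no planned figure to reproduce. What follows is an illustration.

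**Meals on Freedom.** Section 3.2.1 provides three meals a day. Day 1 lunch is on the home pump, and Day 5 breakfast follows the switch-back. That leaves Day 1 dinner (1, bolused) and 3 × 3 = 9 meals on Days 2–4 with boluses discouraged, so 1 of 10 main meals is bolused by design. Snacks are not counted.

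**Inputs from Section 1.1.2.** Time in range on Freedom was 82.4% with boluses and 54.7% without, and 61.8% on the run-in.
- Contrast by bolus status: 82.4 − 54.7 = 27.7 points.
- Gap to run-in: 61.8 − 54.7 = 7.1 points.

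**Assumed clock times (not in the documents).** Freedom starts between 14:00 and 17:00 on Day 1 and ends between 06:00 and 08:00 on Day 5. Time on Freedom is T = (24 − start) + 72 + end, which gives 85 to 90 h.

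**Lift of the pooled figure over 54.7%, for three readings of what counts as bolused:**

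| Reading | Formula | Lift (points) | Pooled value | Share of 7.1 |
|---|---|---|---|---|
| One meal carries a third of the daily contrast | 27.7 × 24 / 3 / T = 221.6 / T | 2.46–2.61 | 57.16–57.31% | 35–37% |
| Freedom start to midnight, b = 7–10 h (8.0–11.4% of T) | 27.7 × b / T | 2.23–3.15 | 56.93–57.85% | 31–44% |
| Freedom start to 06:00 on Day 2, b = 13–16 h (14.9–18.2% of T) | 27.7 × b / T | 4.14–5.04 | 58.84–59.74% | 58–71% |

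The extremes of the third row are 27.7 × 13 / 87 = 4.14 and 27.7 × 16 / 88 = 5.04. This row matches a split at the end of the 23:00–06:00 sleep schedule. It also applies a 24-hour contrast to a stretch that is 44–54% sleep window (7 of 16 h to 7 of 13 h), against 28–29% (21 of 74 h to 21 of 72 h) in the later segment.

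If the true contrast were half as large (13.85 points), the three rows become 1.23–1.30, 1.11–1.57 and 2.07–2.52 points.

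**Home-pump hours.** Assume arrival at 11:00–12:00 and departure 0–2 h after switch-back. This adds 2–8 h, or 2.2–8.6% of the stay. Valued at 61.8%, these hours move the pooled figure (first-row reading) by only +0.10 to +0.39 points.

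**Other endpoints.** Section 1.1.2 gives no hypoglycemia time, CV or SD by bolus status, so no direction can be derived for those.

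**The case against.** The strongest reply is that little depends on this. Section 8.2 sets no hypotheses, the sample is a convenience sample, and the affected outputs are secondary and descriptive. Nine of ten main meals on Freedom already fall under the instruction not to bolus, so the pooled figure is close to the condition of interest. The run-in comparison also sets ordinary life at home against a supervised hotel stay. All of this is correct and limits the weight of the point. It does not supply the missing summary: in a descriptive study the summaries are the result. A cut chosen after seeing data from about ten people is also open to selection.

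A second reply is that the size is unstable. That stands too. It runs from about 2 to about 5 points depending on where the bolused stretch is taken to end, and less if the contrast is smaller.

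A reader might infer three stronger things that the documents do not support.

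- **That a split would make the result directly comparable with 54.7%.** It would not. The earlier figure came from one 24-hour day with large meals, in a fixed order with the bolused day first. Here participants eat as usual for three days.
- **That Days 2–4 are a pure no-bolus condition.** They are not. Section 3.2.3 allows discretionary meal and correction boluses, and Table 1 in Section 3.2.1 allows corrections. How often these occur is unknown in advance.
- **That pooling weakens the safety assessment.** It does not. Counts of severe hypoglycemia and DKA over the Freedom period are the same with or without a split.

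**Conclusion.** The point holds in limited form and should be fixed. The plan mixes two bolus conditions in one hotel summary and omits a summary of the condition that Section 1.2 says the study is to examine further. That follows from the text and needs no assumption.

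The size is uncertain. Using the earlier study's figures, pooled time in range would lie about 2–3 points above the Days 2–4 value (one bolused meal, or bolused time to midnight). It would lie about 4–5 points above if the Day 1 segment runs to 06:00 on Day 2. Either is modest in absolute terms but not small beside a 7.1-point gap. The illustration rests on assumed clock times, on means from ten people without SDs, and on carrying a 24-hour contrast over to part of a day. The home-pump boundary is a wording clarification worth at most 0.4 points on these assumptions.

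**What to change.** In Sections 8.4 and 8.6 and the synopsis:

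1. Define the hotel analysis period for CGM and insulin as time on Freedom, from device start on Day 1 to switch-back on Day 5.
2. Add a prespecified descriptive summary of the CGM endpoints and insulin metrics for the segment with meal boluses discouraged. Fix its start in advance, for example at the end of sleep activity on Day 2, and end it at switch-back. Set it beside the run-in, and state the home versus supervised hotel difference.
3. Report the number of meal and correction boluses given within that segment, so that readers can see how far it departs from no bolusing.
4. Keep the pooled CGM figures as supportive, and keep the safety counts over the whole Freedom period.

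A separate Day 1 column is optional. It should not be compared with the later segment, because it is short and weighted towards sleep.

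The cost is some SAP wording and a few table columns, drawn from device files and a food diary that are already collected. No study procedure changes. The headline time in range may look slightly less favourable.
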